Birmingham site - Patients who are planning to undergo a prostatectomy at UAB will be informed of the study by their urologist at their pre-operative appointment at The Kirklin Clinic. The urologist will put a sentence in his clinic note that the patient has been informed about the study and agreed to have a study coordinator call him with more information. The urology nursing staff will email the study coordinator (secure UAB email to secure UAB email) with the names, MR numbers, and phone numbers of all patients who agree to be called. We will not be conducting any study procedures in The Kirklin Clinic. Our study coordinator will call the patient and explain the study to him. If he agrees to participate, she will conduct an informed consent discussion, answer all the patient's questions and mail the VA consent form, the VA HIPAA and the UAB HIPAA form - Authorization for Use/Disclosure of Health Information for Research form. Should the patient wish to meet in person rather than do a telephone consent, we will meet with them at the TKC Urology Clinic during an already scheduled appointment or at the BVAMC (whatever the patient prefers). If the patient has questions once he receives the consent form in the mail, he can call and have a second discussion with the study coordinator and/or arrange an in-person visit. Should the patient request an in-person visit and provide us with a signed consent form at that visit, we will transport the consent form in a locked bag from The Kirklin Clinic to the Birmingham VAMC.

Philadelphia and Atlanta sites – Recruitment at the Affiliate Urology Clinics at Philadelphia and Atlanta will be developed by the site and approved by their VA and University IRBs as appropriate with local regulations.

Stratification and Randomization

In order to assure between-group comparability, subjects will be stratified on two dimensions with possibility of impacting outcome:

1. Age (<65 years and 65 or older) – older men are more likely to have post-operative incontinence.

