2. Gleason Score (<7 and 7 or greater) - named after Donald Gleason, a pathologist at the Minneapolis VAMC who developed this important tool with other colleagues in the 1960s, to classify the differentiation of the cancer cells in the prostate biopsy; the higher the score, the more anaplastic the tumor pattern, and the more likely that the tumor has spread beyond the prostate. The Gleason score serves as an indication of the likely extent of prostate cancer and serves as a surrogate for the surgical margins that will be necessary to resect the cancer, which will occur after randomization. The more extensive the resections are associated with worse continence outcomes, contingent particularly on whether one or both neurovascular bundles could be preserved. *Seven is considered the cut point for higher risk disease.*

Within each stratum, blocked randomization will be performed using a variable block size and a table of random numbers to avoid inequity in the total number of subjects assigned to each group. Stratification will be used *only* to ensure that the treatment groups are similar on severity and treatment factors, not to compare groups. Each site will have a separate randomization schedule to avoid unequal distributions between sites. Also, blocking is used not to create comparison groups but only to ensure that the groups are similar in size.

Intervention

This telehealth technology allows for daily guidance via a series of interactive screens. At the time of his choosing each day, the participant interacts with a 10-minute session. Informational screens are interspersed with screens that pose questions. Some questions are on understanding of a technique, some on adherence to the rehabilitation program. Depending on the participant's answers, the telehealth program's branching logic permits different paths. For example, if the participant answers that he has not yet resumed his exercises postoperatively, the next screen will inquire about the reason. Four common reasons are listed, and appropriate information and instructions are provided depending on his endorsement of a reason. Some responses, such as repeated failure to resume exercises postoperatively, a lapse in adherence to exercises preoperatively once adherence is established, failure to master a specific skill such as urgency suppression, or

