up or down depending on the error rate detected. Manual inspection of the forms will be done to resolve differences in the dually entered data. The principal investigator and statistician will meet with the database manager to review accrual, data entry, and examine the database for outliers or data base entry errors monthly.

Data Analysis

Preliminary Analyses

Although subjects will be stratified and randomized, the equivalency of the two groups will be evaluated on selected variables that might influence treatment outcome: study site, age, nerve sparing surgery, body mass index. The chi square statistic will be used for the categorical variables and the two-sample t test for continuous variables. Normality will be carefully assessed for continuous outcomes and if the assumption is violated, non-parametric methods will be used.

Outcome Variables Analysis

Primary outcome analysis: duration of incontinence (time to achieve continence after surgery). Participants will be considered continent if they answer that they leak urine “never” on the ICIQ-SF for 3 weeks in a row. Please see Methodology section for complete explanation of this measure. Baseline time for this measure will be the day of surgery. Median time until continence and its 95% confidence interval will be calculated per group. The duration of incontinence will be examined using the Kaplan-Meier procedure, in which all protocol eligible participants are analyzed. Men who did not have a prostatectomy – either due to positive lymph nodes during surgery or because they changed their mind and selected another treatment after randomization but before surgery will not be included in the analysis. All other men randomized will be included. The duration of incontinence will be compared between the 2 groups using the log rank test. We will also compare continence rates at 9 and 12 months.

Secondary outcome analyses (severity of incontinence, impact on quality of life, and patient reported evaluations of improvement and satisfaction with treatment) will be measured by:

1. ICIQ-SF total score
2. EPIC-UI total score
3. Pad use from the EPIC-UI
4. Patient estimation of improvement measured by the GPI and EPI
5. Patient satisfaction as measured by the PSQ
6. IIQ – total and subscale scores
7. IPSS Quality of Life Question (IPSS QoL)
8. Questions on activity restriction, amount of disturbance caused by incontinence
9. Return to work or normal activities after surgery.

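### The primary log-rank test uses none of the randomisation strata; stratifying it by age and Gleason score is a cheap, optional change with a small power gain if those factors are prognostic

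*Combined protocol and SAP*

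**What the plan says.** Under Stratification and Randomization, the plan states that "subjects will be stratified on two dimensions with possibility of impacting outcome". For age (cut at 65) the reason is that "older men are more likely to have post-operative incontinence". Gleason score (cut at 7) serves as a surrogate for how much tissue must be resected: "The more extensive the resections are associated with worse continence outcomes", "contingent particularly on whether one or both neurovascular bundles could be preserved". Site enters through the schedules: "Each site will have a separate randomization schedule to avoid unequal distributions between sites". The same section limits the purpose of stratification: it is used only "to ensure that the treatment groups are similar on severity and treatment factors, not to compare groups".

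Under Data Analysis, Preliminary Analyses, balance is to be checked on "selected variables that might influence treatment outcome: study site, age, nerve sparing surgery, body mass index". Gleason score itself is not listed, although nerve sparing, the main route by which it is thought to act, is. The plan does not say what would be done about an imbalance.

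Under Outcome Variables Analysis, the primary comparison is: "The duration of incontinence will be compared between the 2 groups using the log rank test". No strata or covariates are named. Kaplan-Meier estimates, medians with 95% CIs and continence rates at 9 and 12 months are planned, but no hazard ratio. The Sample size section is also based on a log-rank test without strata.

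**The concern.** When randomisation is stratified on factors thought to bear on the outcome, the usual practice is to carry those factors into the primary test. Stratified blocking makes the arms more alike on these factors than chance would. An unstratified test takes no credit for this, so its variance is too large if the factors are prognostic. The test then rejects less often than its nominal level under the null and can lose some power. In a trial of 156 men, a few points of power may be worth a sentence in the SAP. The choice also has to be made in advance, because a switch made after the data are seen would look data-driven.

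**Working it through.** **The plan's own figure.** Inputs from the Sample size section: 156 men, 1:1, one-sided 0.05, 0.55 versus 0.35 remaining incontinent.

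- Hazard ratio = ln(0.35)/ln(0.55) = 1.756, as stated.
- Expected events = 156 x (0.45 + 0.65)/2 = 85.8.
- Freedman power = Phi(sqrt(85.8) x (1.756 - 1)/(1.756 + 1) - 1.645) = Phi(2.541 - 1.645) = 81.5%, close to the stated 80%. Schoenfeld's formula gives 83.2%.

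So the stated power is reproduced without strata.

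**The comparison.** The stratified statistic is the sum over strata of observed minus expected events, divided by the square root of the summed within-stratum variances. The unstratified test treats all men as one stratum. Both were applied to the same simulated trials, 40,000 per setting.

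Assumptions not in the documents: half the men in each age and Gleason group; three equal sites with one schedule each and no effect on outcome; blocks of 4 or 6 within site x age x Gleason; proportional hazards; weekly event times to week 26; no dropout; and every prognostic hazard ratio. The control arm is set to 55% still incontinent. Two calibrations are used:

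- **A** keeps the plan's marginal 35% in the treatment arm.
- **B** fixes the within-stratum treatment hazard ratio at 1.756. The treatment arm then has 35.7% still incontinent at 1.5/1.5 and 36.8% at 2.0/2.0.

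One-sided power (%), unstratified versus 4 strata (age x Gleason):

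| Hazard ratio, age / Gleason | A unstratified | A 4 strata | Gain | B unstratified | B 4 strata | Gain |
|---|---|---|---|---|---|---|
| 1.0 / 1.0 | 82.8 | 82.4 | -0.4 | 82.7 | 82.4 | -0.3 |
| 1.5 / 1.0 | 83.5 | 83.8 | +0.3 | 81.9 | 82.3 | +0.4 |
| 1.5 / 1.5 | 83.7 | 84.9 | +1.2 | 81.2 | 82.2 | +1.0 |
| 2.0 / 1.0 | 84.2 | 85.6 | +1.4 | 80.3 | 82.1 | +1.8 |
| 2.0 / 2.0 | 84.9 | 88.2 | +3.3 | 77.9 | 82.0 | +4.1 |

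The Monte Carlo standard error of a difference is 0.07 to 0.12 points.

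**Type I error** (one-sided, unstratified versus 4 strata): 4.8 versus 5.1% at 1.5/1.5, 4.5 versus 5.0% at 2.0/1.0, and 4.0 versus 4.9% at 2.0/2.0. The planned test is valid, and conservative when the factors are strong.

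**Other splits.** With 40% aged 65 or older and 70% at Gleason 7 or greater, the gains are +0.8 (A) and +0.7 (B) at 1.5/1.5, and +2.8 (A) and +3.4 (B) at 2.0/2.0. A separate, smaller simulation (4,000 trials per setting, 40% and 65%) shows the same pattern: -0.4 (A) and -0.8 (B) with no effect, +1.0 and +0.9 at 1.5, +4.0 and +3.4 at 2.0. Its standard error is about 0.6 points per power figure.

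**Site.** Crossing age and Gleason with three sites gives 12 strata of 156/12 = 13 men on average. If site has no effect, 12 strata cost about 1.3 points against the unstratified test when nothing is prognostic, and gain nothing at 1.5/1.5 (-0.1). If site hazard ratios are assumed to be 0.67/1/1.5 (10,000 trials, age and Gleason at 1.5), power for unstratified, 4 and 12 strata is 85.5, 86.4 and 87.1% under A, and 79.3, 80.3 and 81.0% under B. With site effects only, stratifying by site alone gives 86.0% against 84.4% for the 4 age x Gleason strata (A).

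**The case against.** The strongest reply is that nothing is broken. The unstratified test is valid, agrees with the sizing and targets the same marginal effect as the Kaplan-Meier curves and medians. All of that stands.

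It can also be said that the plan has already decided the matter by stating that stratification is used only "to ensure that the treatment groups are similar on severity and treatment factors, not to compare groups". That can be read as keeping strata out of the analysis. The more natural reading is that it rules out comparing one stratum with another, which a stratified treatment test does not do. The wording is open enough to need a clarifying sentence.

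Third, the plan speaks only of a possible effect on outcome, and Gleason score acts through a surrogate. This stands: a reader might infer that the plan expects both factors to be prognostic, but the text supports that for age more than for Gleason. The range above therefore includes no effect, where stratifying costs a little.

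Finally, if the analysis should mirror the randomisation, site belongs in it too, and Preliminary Analyses lists site among the variables that might influence outcome. This also stands. Leaving site out of the primary strata is a choice to avoid sparse cells. The figures above do not show it to be best if site is prognostic.

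**Conclusion.** The point holds as an optional, low-severity improvement. The gain depends wholly on assumed prognostic effects: a loss of about 0.3 to 0.5 points if neither factor matters, about +1 point at 1.5 for both, and about +3 to +4 points at 2.0 for both.

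Two stronger readings are not supported. A reader might infer that the plan contradicts itself or that its test is invalid; the test matches the sizing and its error rate stays at or below nominal. A reader might also infer from the 77.9% in the table that the trial is underpowered. That figure arises only if 1.756 is taken as the within-stratum effect, which leaves 36.8% of the treatment arm incontinent. The Sample size section instead derives 1.756 from the marginal 0.55 and 0.35. With those held, the unstratified test stays at 82.8% or above in every setting of the table.

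The absence of a planned hazard ratio is a separate reporting point and not a reason to stratify.

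**What to change.** Before any unblinded comparison:

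- Specify the primary test as a log-rank test stratified by age group x Gleason group (4 strata).
- Report a hazard ratio with 95% CI from a Cox model stratified the same way, so that test and estimate match. Describe it as conditional and not identical to the marginal 1.756: under calibration A, the within-stratum value is 1.789 at 1.5/1.5 and 1.857 at 2.0/2.0.
- Keep the unstratified log-rank test as a sensitivity analysis and add one that includes site, for example a site-adjusted Cox model. State that site is left out of the primary strata to avoid sparse cells.
- Clarify in Stratification and Randomization that the restriction on comparing groups refers to between-stratum comparisons.
- If the sponsor prefers the unstratified test, say so and give the reason.

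The strata are recorded at randomisation, so no new data are needed. The costs are the small power loss if neither factor is prognostic, and a conditional hazard ratio reported beside marginal curves and medians.

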This will be a randomized controlled trial of telehealth administration of an evidence-based perioperative pelvic floor muscle training program versus an attention control condition to reduce the severity and duration of post-prostatectomy urinary incontinence. The primary outcome will be time to continence (date of surgery until no leakage reported for 3 weeks in a row). Related symptoms, severity of incontinence, condition-specific quality of life, and patient assessment of outcome and satisfaction will be measured as secondary outcomes. The telehealth program was developed and pilot tested with RR&D grant funding and was well accepted by Veterans. The telehealth device used in the pilot study was a Health Buddy™ (Bosch Inc. – Figure 4) which is used widely throughout the VA in the Care Coordination / Home Telehealth (CCHT) program.¹¹ Bosch is exiting the telehealth industry as of May 15, 2015 but has agreed to follow research participants currently in the program until March 15, 2016. The program, with the branching logic will be transferred to similar technology with another VA approved telehealth vendor. One of the advantages of telehealth programs is the capability to have branching logic, so that the program is individualized depending on the progress and symptoms of the Veteran as he is progressing through each day's session.

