The control group is designed to control for the daily use of a telehealth program (an attention control) as well to equate basic information about urinary incontinence between groups. The control program matches the number of interactions but is limited to general prostate cancer information; perioperative care; wetness, odor and skin care management but no content on pelvic floor muscle training and bladder control strategies. Outcome measures will be administered by the telehealth program in both groups. For the Health Buddy, data are stored on the telehealth program and transmitted each night via toll-free telephone lines to a database behind a secure VA firewall as they are in the CCHT program. This was proven to be feasible and practical in our pilot study. For the web-based program, the data will be stored on a secure website with VA-approved encryption. Both groups will have use of the telehealth program monitored and quantitated. Preoperatively and 2 months postoperatively, telehealth sessions will be daily. After 2 months postoperatively, both groups will log-in weekly for outcomes measurement until 6 months postoperatively and two more times at 9 & 12 months postoperatively. If we cannot obtain a response through the telehealth program, the questionnaires will be mailed to the participants along with a postage-paid return envelope. These measures are delineated in detail in the Outcome Measures section and in Table 5. The telehealth content for each session for both groups ends with a "fun fact" including sports and other trivia, famous men who have done well after prostate cancer diagnosis, etc. which have been successfully implemented in the pilot study and promoted adherence to the daily home telehealth program, in our pilot study as well as in the CCHT programs VA wide. At 12 months, Veterans still incontinent in both groups will be offered treatment in the GRECC Continence Clinics or the VA Urology Clinic.

THEORETICAL FOUNDATION

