Intensive protocol training will be done for the project managers at both sites as well as for the nurse interventionist. This will occur on-site for both the Atlanta and Birmingham sites, and then be supplemented by weekly VANTS calls to prevent procedure drift and discuss problems as they arise, The PI is also available any time by cell phone to answer more urgent questions. On the weekly calls, we will review results of the interventions by the study coordinators for participants who are non-adherent to conducting their daily telehealth sessions. The nurse interventionist in Birmingham will be conducting all telephone interventions for participants at all sites who are completing their telehealth session, but not meeting learning goals. A formal monthly meeting will be conducted with the PI and nurse interventionist to review all telephone support, including content and results. Because the nurse interventionist's and the PI's offices are close together in the Birmingham office of the GRECC, we also anticipate being able to discuss these calls immediately after they occur as well.

Follow-Up

After completing the daily 2-month post-operative program, participants will complete an outcome assessment once a week until 6 months after their surgery, and then again at 9 and 12 months. Weekly, this will be the ICIQ-UI short form, and every 4 weeks the EPIC-UI and the EPI, GPI, and PSQ will be added as outlined in **Table 4**. Specifics for these measures are in the following section on Outcome Measures. For the 9- and 12-month outcomes assessment, a questionnaire will be mailed with a post-paid, pre-addressed envelope only if the patient does not respond to the telehealth session. If participants in either group do not do a weekly assessment, they will be called to prompt them to complete the assessment or offered the opportunity to complete it on the telephone.

Table 4 – Data Collection Schedule						
	Pre-op Visit	1 Month After Discharge	Ongoing in the 6-Month Post-op period	At 6 Months Post-op	At 9 Months Post-op	At 12 Months Post-op
CPRS Abstraction	H & P	Hospital Record				CPRS Clinic Notes and Medication Profile
Continence History	X					
ICIQ-UI-SF [4 items]	X		WEEKLY via telehealth program	X	X	X
EPIC-UI [4 items]	X		MONTHLY via telehealth program	X	X	X
IIQ-SF, IPSS QoL question, other QoL questions [11 items]	X**		MONTHLY via telehealth program		X	X

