The primary patient outcome is time to continence as measured by the ICIQ-SF. The ICIQ-SF is designed, in part, to screen for incontinence and is completely appropriate to determine if a person no longer has incontinence. We used time to continence in our previous clinical trial of preoperative training to prevent post-prostatectomy incontinence.⁴ Time to continence also has face validity since it is extremely important to the patient who wants to regain continence as soon as possible after his surgery. The ICIQ-SF will be completed weekly for 6 months post-operatively via the telehealth program. Each telehealth screen related to the ICIQ-SF will be prefaced with "During the last week" to make the timeframe clear. When a participant reports no incontinence on the ICIQ-SF (an answer of "never" to "In the last week, how often did you leak urine?") for 3 weeks in a row, we will consider him continent. We successfully used the definition of no reported leakage for 3 weeks based on weekly bladder diaries in our prior study of preoperative training to prevent post-prostatectomy incontinence.⁴ Although it is likely that participants who achieve this endpoint may still have occasional leakage, such as with heavy lifting or a good laugh, experience has shown that these men do not consider themselves incontinent. The total score of the ICIQ-SF will also be used to evaluate patient outcomes. The ICIQ-SF score has shown sensitivity to change with treatment in men with post-prostatectomy incontinence.²⁶ We will also compare continence rates at 9 and 12 months.

Secondary Outcome Measures

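### Can continence rates be compared at 9 and 12 months when each visit has one weekly report and the written definition of continent needs three in a row?

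*Combined protocol and SAP*

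**What the plan says.** The primary outcome is time to continence. The Overview under Research Strategy defines it as "date of surgery until no leakage reported for 3 weeks in a row". The Outcome Measures section ties the same rule to the weekly ICIQ-SF: when a man answers *never* to the question on leakage in the last week "for 3 weeks in a row, we will consider him continent". The primary outcome paragraph in Data Analysis repeats the rule.

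On the schedule, the Overview says that after the second postoperative month "both groups will log-in weekly for outcomes measurement until 6 months postoperatively and two more times at 9 & 12 months postoperatively". The Follow-Up section and Table 4 agree: one ICIQ-SF at 9 months and one at 12. The fallback for these visits is a single form: "For the 9- and 12-month outcomes assessment, a questionnaire will be mailed with a post-paid, pre-addressed envelope only if the patient does not respond".

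Outcome Measures and Data Analysis both add the later comparison: "We will also compare continence rates at 9 and 12 months". Neither says how a man is scored at those visits. Outcome Measures does call the ICIQ-SF "completely appropriate to determine if a person no longer has incontinence".

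**The concern.** Read strictly, the plan promises a comparison that its own definition cannot support. Continent means three weekly reports in a row, and each late visit supplies one report with a one-week recall. The neighbouring reports are about 13 weeks away.

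Three things would be at stake. First, an analyst would have to choose a rule later, possibly after seeing data. Second, the word continent would carry two meanings in one report: a sustained three-week state for the primary outcome and a one-week state for the late rates. Third, if a three-week state was intended at the late visits, the unrecorded weeks could not be recovered. The late rate is also the only analysis for which the Data Analysis section names month 9, since the score and global-rating regressions are at 6 and 12 months.

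**Working it through.** **The plan's own figure.** The plan states no number for the late rates. Its one calculation on continence is in Sample size: 156 men, 0.55 versus 0.35 remaining incontinent, one-sided 0.05, 80% power.
- Hazard ratio = ln(0.35)/ln(0.55) = 1.756, as stated.
- Expected events = 156 × (1 − 0.45) = 85.8, where 0.45 is the mean of 0.55 and 0.35.
- Freedman power = Φ(√85.8 × 0.756/2.756 − 1.645) = 81.5%, close to the stated 80%.

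No 9- or 12-month scoring rule enters this calculation.

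**Reports needed against reports scheduled.** The definition needs 3 consecutive weekly reports. The schedule gives 1 at 9 months and 1 at 12 months. Months 6, 9 and 12 are about 52/4 = 13 weeks apart.

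**The possible readings of a late rate.**

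| Reading | Result from the scheduled data |
|---|---|
| Three-week status at the visit | 1 of 3 reports is available, so no man can be scored and there is no rate |
| Ever met the three-week rule, carried forward | No new event is possible after month 6, so both late rates equal the month-6 rate |
| *Never* on the single report at the visit | Every responder can be scored, and the rate reflects status at that visit |

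The first reading gives nothing, and the second makes the late ICIQ-SF irrelevant to the rate. Only the third uses the data the plan collects.

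**How far the third reading could differ from a three-week status.** In the same men with all three reports, a single *never* gives an equal or higher rate, because it is one of the three conditions. The order is not guaranteed if the two rules are scored on different complete cases.

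For illustration only, assume that weekly answers are independent within a man. A man with weekly probability p of *never* then meets the single-report rule with probability p and the three-week rule with p³. Suppose dry men have p = 0.98, occasional leakers have p = q, and the rest have p = 0:
- 45% dry, 15% occasional, q = 0.5: single 0.45 × 0.98 + 0.15 × 0.5 = 0.516; three-week 0.45 × 0.98³ + 0.15 × 0.5³ = 0.442; gap 7.4 points.
- 65% dry, 20% occasional, q = 0.7: single 0.65 × 0.98 + 0.20 × 0.7 = 0.777; three-week 0.65 × 0.98³ + 0.20 × 0.7³ = 0.680; gap 9.7 points.

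These shares and probabilities are assumptions; the documents supply none. The gap concerns the level of a rate within a group. Both arms are scored by the same rule, so the randomised comparison of one-week status remains valid.

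**Cost of forcing the three-week rule onto the late visits.** Two extra weekly prompts before each of two visits for 156 men is 2 × 2 × 156 = 624 prompts. If each report is missing independently with probability m, the share without a full set of three is 1 − (1 − m)³:
- m = 5%: 14.3%, about 22 of 156 men, against about 8 with one report.
- m = 10%: 27.1%, about 42 men, against about 16.
- m = 20%: 48.8%, about 76 men, against about 31.

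The values of m are assumed. If missed reports cluster within men, these shares overstate the loss. In any case the mailed form can supply only one of the three reports.

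**The case for a change.** The strongest case for a change is this. The Data Analysis section defines continent without limiting the definition to the time-to-event endpoint, and it does so in the paragraph that promises the late rates. The team chose three weeks deliberately, following its earlier trial, and Table 1 notes that leakage varies with activity, so one good week is weaker evidence. No section adopts a single *never*. The Overview says "At 12 months, Veterans still incontinent in both groups will be offered treatment", which is status wording, while Follow-Up describes the same men as not having reached continence by that time, which leans towards an ever-achieved reading. One sentence would settle it.

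Part of this stands. The visit-level rule is unwritten, and a one-week rate is a different measure from the primary endpoint. A report should label it so and should put any month-6 rate shown beside it on the same one-week basis, which the weekly reports already allow.

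The rest carries less weight. The two sentences about men at 12 months say who is offered clinic treatment and are not analysis rules. The room for a choice made after seeing data is small, because of the three readings one yields no rate and one yields no new information. Nothing in the documents shows that a sustained three-week state is needed at the late visits, and collecting it would be a debatable trade of extra contacts and incomplete sets for a matching label. Writing the single-report rule into the plan would do no harm, but it would record what an analyst would do anyway.

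**Conclusion.** The observation is accurate, but it is missing detail and not a fault in the design. The scheduled data support a valid between-arm comparison of one-week continence at 9 and 12 months, and the natural scoring rule follows from the item collected. The late rates may sit above a three-week status, by about 7 to 10 points under the assumed mixes. That size cannot be derived from the documents, and the direction is certain only in the same men with complete reports. The primary log-rank test, the sample size of 156 and the score analyses at 6 and 12 months are untouched. The conclusion assumes that the late rates are read as status at the visit, scored identically in both arms and described as such. No change to the plan follows.
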